6.2 Secondary Objectives

The secondary objective is to characterize IUS prescribing practices, utilization patterns of Levosert, and level of satisfaction with Levosert for the indications of contraception and menorrhagia amongst prescribing OB-GYNs in the selected countries.

7 METHODOLOGY

This is a retrospective cross-sectional study collecting secondary data on the experience of OB-GYNs who prescribe Levosert in four (4) European countries: Czech Republic, Poland, Serbia, and Slovakia.

Respondents are healthcare providers (HCPs) who have their primary specialization in obstetrics and gynaecology. Hereinafter, this document shall refer to the respondents, who are prescribers of Levosert, as Prescribers. Refer to Section 8.1 for Prescriber eligibility criteria.

The survey will be fielded through an online survey platform tool and data will be stored in a cloud-based environment. The questionnaire will collect quantitative data by means of closed-ended questions.

Prescribers will be asked to report their real-world experience with Levosert in patients who have used or are still using the drug for contraception and HMB (with and without intended contraception). Prescribers will be asked to report about all the patients they have managed with Levosert (including numbers of Levosert prescriptions and replacements or removals). Individual patient data will not be reported. Instead, data will be considered aggregate and will be fully anonymous.

7.1 Discussion of Study Design

[figure not shown]
This is a cross-sectional study where Prescribers complete the questionnaire only once. Responding to the questionnaire is expected to take not more than twenty (20) minutes.

The sample target is 380 respondents, with the sample distribution guided by expected available OB-GYN respondents in a large physician panel that is active in the study countries.

The estimated duration of the study (from EC submission through reporting) is approximately 1 year (see Figure 1). The duration of survey fielding is up to 4 weeks per country.

13-02-2023 This document is confidential.

Figure 1. Study Design

^{*} Survey fielding will be staggered dependent on the timing of the EC Approval.

7.2 Survey Population

This DUS will be conducted with Prescribers and will be approved by an ethics committee (EC) in each participating country prior to implementation. Prescribers who successfully complete the screener (i.e., who are not terminated based on any of the screening questions) quality to complete the questionnaire. All Prescribers will be asked to respond to the same closed-ended questions, translated into the language predominantly spoken in the country of their practice location (i.e., Czech in Czech Republic, Serbian in Serbia, Slovakian in Slovakia, and Polish in Poland).

The sample of Prescribers will be selected from a pool of potentially eligible OB-GYNs in a large physician panel that is active in the selected four countries.

Page 15 of 35

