6.1 Primary Objective

The primary objective is to describe the duration of Levosert utilization for the indications of contraception and HMB (with and without intended contraception) amongst prescribing OB-GYNs in the selected countries.

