8.1.1 Inclusion Criteria

- HCP has its primary practice located in Czech Republic, Poland, Serbia, or Slovakia
- HCP's primary state-certified medical specialty is Gynaecology and Obstetrics.
- HCP spends at least 25% of their professional time in direct patient care, as opposed to teaching, research, or administrative roles
- HCP has prescribed Levosert for HMB to at least two (2) patients
- HCP has removed or replaced Levosert from at least one (1) patient who received the product for HMB

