10.1 Primary Endpoint Definition

The primary objective of this study is to describe the expected real-world usage duration of Levosert for its different indications.

Duration of Levosert usage is defined as the difference in time between removal (with or without replacement) and insertion of the device. In the absence of detailed patient-level data and in the context of this survey, expected duration of Levosert usage for each indication will be calculated as follows:

Expected usage duration of Levosert (years)

$$= \sum_{i=1}^{6} (i \ x \ likelihood \ of \ Levosert \ removal \ in \ Year \ i)$$

+ (likelihood of Levosert removal beyond Year 6 x total expected usage duration in those patients)

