Appendix 2: Screener

S1. In which country is your primary practice located?

1	Poland	POLAND QUOTA=150
2	Czech Republic	CZECH REPUBLIC QUOTA=80
3	Serbia	SERBIA QUOTA=100
4	Slovakia	SLOVAKIA QUOTA=50
98	Other (specify)	TERMINATE

S2. What is your role within your practice?

1	Physician	CONTINUE
2	Nurse	TERMINATE
98	Other (specify)	TERMINATE

S3. What is your primary state-certified medical specialty?

1	General Practice/Internal Medicine	TERMINATE
2	Dermatology	TERMINATE
3	Endocrinology	TERMINATE
4	Gynecology and Obstetrics	CONTINUE
98	Other (specify)	TERMINATE

S4. Approximately what percent of your professional time is spent on direct patient care, as opposed to teaching, research, or administrative roles?

1	Less than 25% of the time	TERMINATE
2	25-50% of the time	CONTINUE
3	51-75% of the time	CONTINUE
4	More than 75% of the time	CONTINUE

S5. How many years have you been practicing Gynecology and Obstetrics since gaining this specialization?

1	0 - 3 years	TERMINATE
2	4 - 10 years	CONTINUE
3	11 - 20 years	CONTINUE
4	More than 20 years	CONTINUE
97	I am not a certified specialist yet	TERMINATE

S6. Which of the following intrauterine systems (IUSs) have you prescribed to your patients? *Please select all that apply.*

1	Levosert (levonorgestrel)	TERMINATE IF NOT SELECTED
2	Mirena (levonorgestrel)	
3	Skyla (levonorgestrel)	
4	Liletta (levonorgestrel)	
98	Other [ANCHOR]	

S7. Which of the following intrauterine systems (IUSs) do you have experience removing (with or without replacement)?

Please select all that apply.

1	Levosert (levonorgestrel)	TERMINATE IF NOT SELECTED
2	Mirena (levonorgestrel)	
3	Skyla (levonorgestrel)	
4	Liletta (levonorgestrel)	
98	Other [ANCHOR]	
97	None [ANCHOR, EXCLUSIVE]	

S8. In the past **10 years**, approximately how many intrauterine systems (IUSs) have you prescribed?

#	TERMINATE IF < 2
π	TEMVIIIVATE II \ Z

S9. Since **Levosert (levonorgestrel)** has been available in your country, for approximately **how many** patients have you prescribed and removed (with or without replacement) Levosert (levonorgestrel)?

	Contraception only	Heavy menstrual bleeding (with and without intended contraception)
Total number of Levosert prescriptions	#	# TERMINATE IF < 2
Total number of Levosert removals (with or without replacement)	#	# TERMINATE IF = 0

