Q12. Overall, how satisfied are you with **Levosert (levonorgestrel)** in patients who use it **for three or more years** for the following indications?

	Contraception only	Heavy menstrual bleeding (with and without intended contraception)
Not at all satisfied	1	1
Not very satisfied	2	2
Somewhat satisfied	3	3
Very satisfied	4	4
Do not have enough experience to rate	99	99

Q13. What is the recommended duration of use of Levosert (levonorgestrel) for heavy menstrual bleeding (with and without intended contraception) in your country?

1	3 years	
2	4 years	
3	5 years	
4	6 years	
99	Do not know	

In closing, we would like to ask you a few last questions about your practice	
---	--

Q14. Please enter the postal code of the practice setting where you spend the majority of your time?

Q15. Which of the following best describe the practice setting where you spend the majority of your time?

1	Hospital-based/inpatient practice	
2	Multi-specialty outpatient practice, including OB/GYN specialty	
3	Single specialty outpatient OB/GYN practice	
98	Other	

Thank you for your time! Please read this and make sure to click the arrow button below to submit your survey.

If you are aware of individual adverse reactions with **Levosert (levonorgestrel)** that were not reported previously, please kindly report them to the national reporting system of your practice location or the drug safety contact of the Sponsor!

Contact details of the national reporting system and the Sponsor for your primary practice location:

Poland	National Reporting System
	Departament Monitorowania Niepożądanych Działań Produktów Leczniczych Urzędu Rejestracji Produktów Leczniczych, Wyrobów Medycznych i Produktów Biobójczych
	[name]
	[name]
	Tel.: [name]
	Faks: [name]
	https://smz.ezdrowie.gov.pl
	Sponsor Drug Safety Contact
	Gedeon Richter Polska Sp. z o.o.
	E-mail: [contact]
	[contact]
	https://www.gedeonrichter.pl/zgloszenie-dzialania-niepozadanego/
Czech Republic	National Reporting System
	Státní ústav pro kontrolu léčiv
	[name]
	[name]
	http://www.sukl.cz/nahlasit-nezadouci-ucinek
	Sponsor Drug Safety Contact
	Gedeon Richter Marketing ČR, s.r.o.
	[name]
	[name]
	E-mail: [contact]
	[contact]
	https://www.richtergedeon.cz/hlaseni-nezadoucich-ucinku/
Serbia	National Reporting System
	Medicines and Medical Devices Agency of Serbia

13-02-2023 This document is confidential.

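### The contraception-only items behind the primary endpoint (Q7, Q8) have no experience requirement, routing or opt-out, so answers not based on any patients can enter that estimate

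*Protocol*

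**What the plan says.** Section 6.1 covers both indications: the aim is to "describe the duration of Levosert utilization for the indications of contraception and HMB". Section 10.1 says that the "expected duration of Levosert usage for each indication will be calculated as follows", and gives a sum over Years 1 to 6 plus a term for use beyond Year 6. The yearly likelihoods come from Q7. The beyond-Year-6 duration comes from Q8 (contraception only) and Q9 (HMB).

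The two experience criteria in section 8.1.1 concern HMB alone: "HCP has prescribed Levosert for HMB to at least two (2) patients" and "HCP has removed or replaced Levosert from at least one (1) patient who received the product for HMB". Screener S9 (Appendix 2) collects prescriptions and removals for both indications, but only the two HMB cells carry a termination rule. S6 and S7 ask about Levosert in general, so HMB cases alone satisfy them.

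Section 7.2 then states: "All Prescribers will be asked to respond to the same closed-ended questions". In Appendix 3, Q7 asks for six cumulative percentages per indication and Q8 accepts 7 to 10 years. Neither shows a skip rule or a no-experience code. Q12, on satisfaction, offers one in both columns: "Do not have enough experience to rate".

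**The concern.** A prescriber whose S9 entries for contraception only are both zero qualifies and is shown the contraception columns of Q7 and Q8. The instrument gives that person no valid way to report having no such patients. Two features encourage filling the cells anyway: the closing text of the screener asks for answers that are as complete as possible, and section 11.3 withdraws payment if the survey is ended early.

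At stake is the contraception half of the primary objective. Answers without patients behind them would count towards its n, narrow its confidence interval without adding information, and could move the estimate.

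**Working it through.** **1. Reproducing the plan's own figures (Appendix 1, Table 3).** Expected removals = quota × estimated removals ÷ practising OB-GYNs.

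- Czech Republic: 80 × 7,400 / 2,600 = 227.7
- Poland: 150 × 16,900 / 5,900 = 429.7
- Serbia: 100 × 1,100 / 1,600 = 68.8
- Slovakia: 50 × 2,100 / 1,100 = 95.5

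The total is 821.6. Multiplied by 0.55 it is 451.9, and by 0.45 it is 369.7. Table 3 gives 821, 452 and 369, so the figures reproduce.

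**2. Respondents with no contraception-only prescriptions.** These are the people with no such patients at all. Assumptions: sales stand for prescriptions, the 45% split applies to them, and counts are Poisson around the country average. Mean = 0.45 × sales ÷ OB-GYNs; expected zeros = quota × exp(−mean).

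| Country | Mean | Expected zeros |
|---|---|---|
| Czech Republic | 0.45 × 27,800 / 2,600 = 4.81 | 0.7 of 80 |
| Poland | 0.45 × 55,300 / 5,900 = 4.22 | 2.2 of 150 |
| Serbia | 0.45 × 4,400 / 1,600 = 1.24 | 29.0 of 100 |
| Slovakia | 0.45 × 8,800 / 1,100 = 3.60 | 1.4 of 50 |

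The sum is about 33 of 380, or 9%.

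**3. Respondents with no contraception-only removals.** This is a wider group, and some of its members have current contraception users.

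- Poisson with mean 0.45 × removals per OB-GYN gives zero probabilities of 0.278, 0.276, 0.734 and 0.424 (countries in the same order). Expected zeros are 22 + 41 + 73 + 21, or 158 of 380 (42%) before rounding by country.
- To let a physician's HMB and contraception volumes move together, a gamma-mixed Poisson with shape k can be conditioned on at least one HMB removal. With m the mean removals per OB-GYN and L(t) = (1 + mt/k)^(−k), the share with none is [L(0.45) − L(1)] / [1 − L(0.55)]. For k = 0.5, 1 and 2 this gives 138, 148 and 154 of 380 (36%, 39% and 41%).

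**4. How the formula treats an all-zero column.** Six zeros pass the Q7 validation, which only requires that entries do not fall. The likelihood beyond Year 6 is then 100%, so the respondent's expected duration equals the Q8 entry, 7 to 10 years.

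For scale, take the retention figures in Appendix 1 (0.94, 0.87, 0.82, 0.76, 0.65). Years 1 to 5 contribute 0.06×1 + 0.07×2 + 0.05×3 + 0.06×4 + 0.11×5 = 1.14 years. If the remaining 65% are removed in Year 6, the total is 1.14 + 0.65×6 = 5.04 years. If a share f of respondents enters all zeros, an unweighted mean rises by f × (7 − 5.04) to f × (10 − 5.04):

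- f = 9%: 0.18 to 0.45 years
- f = 40%: 0.8 to 2.0 years

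This is an illustration only. Not everyone without experience would enter zeros, and removal later than Year 6 would raise the baseline and reduce the shift.

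**5. The opposite path.** A respondent who copies the HMB column into the contraception column pulls the two estimates together.

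**The case against.** **Forced response is not stated.** A reader might infer that respondents must answer and that invented answers will enter. Section 7.2 says only that they are asked, and the sentence goes on to translation. Section 9.2 leaves validation to survey programming. This stands: such answers can enter, but the protocol does not show that they will.

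**No removals is not the same as no patients.** A reader might take the 42% as the share with no contraception patients. It is not. Section 7 covers patients still using the device, and a prescriber with such users has relevant experience. The matching figure is about 9%.

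**Table 3 gives no floor.** It expects 31 contraception-only removals among 100 Serbian and 43 among 50 Slovak respondents. A reader might conclude that at least 69 + 7 = 76 of 380 (20%) have none. But Table 3 averages over all practising OB-GYNs. It also expects only 38 HMB removals for the 100 Serbian respondents, each of whom must have at least one. It cannot describe the eligible sample, and the true share could be well below 20%.

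**A shrunken difference is not established.** Step 4 shows a path that would lengthen the contraception estimate instead.

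**Q8 or Q9 after 100% removal by Year 6 does not touch the primary endpoint.** The term is multiplied by zero. Only item 15 of section 10.3 is affected. Q5 and Q11 do not enter the primary endpoint either.

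**The analysis could handle it.** S9 identifies zero-count respondents, and an analysis plan not shown here could exclude them or weight by S9 counts. This stands in part. No analysis rule can add an opt-out after a single completion, nor tell a considered answer from a guess by someone with a few users.

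**The regulatory question concerns HMB.** HMB answers do come from prescribers screened for HMB experience, and the study is descriptive. That limits the consequence, but contraception duration is still named in the primary objective.

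**Conclusion.** The point holds as a gap in the instrument. As written, the questionnaire allows answers with no contraception-only patients behind them into half of the primary endpoint, and gives those respondents no valid alternative. Having an opt-out for satisfaction but not for the items that feed the primary endpoint is hard to justify.

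The size is unknown. On the protocol's averages, about 9% of respondents would have no contraception-only prescriptions and up to about 36–42% no contraception-only removals. These figures rest on the Poisson or gamma-Poisson spread, the 45% split and, for the 9%, on sales standing for prescriptions. Both are probably too high, because eligible prescribers are likely heavier users than the average OB-GYN. The 36% figure already allows for this in part by conditioning on an HMB removal. The direction of bias cannot be stated in advance. The change is cheap and worth making before fielding.

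**What to change.** - Show the contraception-only column of Q5 and Q7, and show Q8, only if the S9 contraception prescription count is above 0. Show that column of Q11 only if the S9 contraception removal count is above 0.
- Add Q12's code 99 to Q7, Q8 and Q9, for prescribers who have users but too little experience to answer.
- Show Q8 and Q9 only if the matching Q7 entry for Year 6 is below 100%. This tidies item 15 of section 10.3 and leaves the primary endpoint unchanged.
- Amend section 7.2 to match.

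The cost is survey programming and ethics committee approval of the revised questionnaire in each country, as section 11.2 requires. The contraception estimate will also rest on fewer respondents. On the figures above, about 380 − 33 = 347 would be shown Q7 for contraception, with some of them choosing code 99. The expected 369 contraception-only removals are not reduced by the routing, because the respondents routed out contribute none.

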8 SELECTION OF SURVEY POPULATION

8.1 Prescriber Eligibility Criteria

Prescribers will be selected from a large physician panel that is active in the study countries. This process will be managed by the study coordinating centre.

8.1.1 Inclusion Criteria

- HCP has its primary practice located in Czech Republic, Poland, Serbia, or Slovakia
- HCP's primary state-certified medical specialty is Gynaecology and Obstetrics.
- HCP spends at least 25% of their professional time in direct patient care, as opposed to teaching, research, or administrative roles
- HCP has prescribed Levosert for HMB to at least two (2) patients
- HCP has removed or replaced Levosert from at least one (1) patient who received the product for HMB

8.1.2 Exclusion Criteria

- HCP is not a physician
- HCP never prescribed Levosert
- HCP or any member of the HCP's household is affiliated with or employed by any pharmaceutical companies as a consultant and/or researcher (other than participating in clinical studies or clinical investigations)

8.2 Randomization

Only Prescribers who meet all screening criteria will be admitted to the survey. There is no randomization by any HCP characteristic.

8.3 Risk and Benefit

This DUS will be directed towards Prescribers. Patients will neither be contacted, nor will they be exposed to any additional risk because of this study. Also, this study does not intend to collect any patient-level data, including any personal data. For the Prescribers, there are no foreseeable risks or discomforts associated with participation in this study, however, there is always a possible risk of loss of confidentiality. The research team has safeguards in place to ensure that the confidentiality of the Prescribers is guaranteed. No Prescriber identifiable data will be shared by the panel provider with the Study Coordinating Centre, Sponsor, or any other third party.

8.4 Study Withdrawal, Removal, and Replacement of Prescribers

All Prescribers have the right to withdraw from or terminate the DUS for any reason and at any time during the study (i.e., during the screening process or on-line survey completion). Prescribers who prematurely discontinue the DUS will be replaced. If, for whatever reason, a Prescriber withdraws from the DUS no further action will be initiated other than the recruitment of a replacement.

This document is confidential.

9 DATA MANAGEMENT AND QUALITY CONTROL

9.1 Data Handling

Data will be collected on a real-time basis using a cloud-based platform for creating and distributing web-based surveys.

The platform is GDPR (General Data Protection Regulation) compliant. The collection of personal data of participating Prescribers will be limited to the amount necessary to achieve the aims of the research and to compensate the respondents, so that no unneeded sensitive information is being collected. No responses will be attributed to individual Prescribers, and all data will be reported in aggregate form. No patient-level data (e.g., from healthcare records) will be collected as part of this DUS. De-identified data will be sent to the Study Coordinating Centre for statistical analysis.

Data will only be collected in electronic form and no hard copy documents will be retained. The electronic data records will be stored in a password-protected, cloud-based environment.

9.2 Quality Control

Quality Control and Quality Assurance will be achieved through data validation provisions applied to the programming of the survey, which is the responsibility of the Study Coordinating Centre. The Study Coordinating Centre will also be responsible to ensure that the DUS is conducted in accordance with the protocol and monitor data accrual on an ongoing basis.

13-02-2023 This document is confidential. Page 16 of 35

10 STATISTICAL METHODOLOGY

This section provides an overview of the statistical methods that will be applied to answer the research questions. This is a descriptive study without any hypotheses being tested.

10.1 Primary Endpoint Definition

The primary objective of this study is to describe the expected real-world usage duration of Levosert for its different indications.

Duration of Levosert usage is defined as the difference in time between removal (with or without replacement) and insertion of the device. In the absence of detailed patient-level data and in the context of this survey, expected duration of Levosert usage for each indication will be calculated as follows:

Expected usage duration of Levosert (years)

$$= \sum_{i=1}^{6} (i \ x \ likelihood \ of \ Levosert \ removal \ in \ Year \ i)$$

+ (likelihood of Levosert removal beyond Year 6 x total expected usage duration in those patients)

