Appendix 1: Supporting Data for HCP Sample Size Determination

A feasibility assessment was conducted to understand the estimated number of Levosert removals since product launch in each country, the total number of practicing OB-GYNs, and the expected number of OB-GYNs that could be recruited from a large physician panel across the study countries (i.e., OB-GYNs who would be eligible and willing to participate).

The number of Levosert removals in the countries of interest has been estimated from:

- 1. The number of pharmacy-level Levosert sales per country and per year from product launch in 2014 until the last full year of product sales which is 2020 (IMS pharmacy sales database, 2021).
- 2. LNG-IUS user retention after 1 to 5 years of usage as reported by a post-marketing study: 0.94, 0.87, 0.82, 0.76, 0.65, respectively (Backman et al., 2001). For years outside the reported years, 0% retention is assumed resulting in a conservative estimate.

Table 2. Levosert Removals Sin	ce Proc	luct Lau	nch, Es	stimatio	n
Country	2020	2019	2018	2017	- 2

	Country	2020	2019	2018	2017	2016	2015	2014	Total
Czech	Sold	5,803	5,320	5,206	4,233	4,326	2,768	99	27,755
Republic	Removed since (estimated)	348	692	937	1,016	1,514	2,768	99	7,374
	Sold	8,736	11,765	8,971	9,282	8,619	7,931	40	55,344
Poland	Removed since (estimated)	524	1,529	1,615	2,228	3,017	7,931	40	16,884
	Sold	690	907	805	794	907	323	0	4,426
Serbia	Removed since (estimated)	41	118	145	191	317	323	0	1,135
	Sold	1,771	1,824	1,733	1,469	1,485	549	3	8,834
Slovakia	Removed since (estimated)	106	237	312	353	520	549	3	2,080
τ	Jser retention (estimated)	94%1	87%²	82%2	76%²	65%²	0%	0%	

The number of practicing OB-GYNs per country has been estimated based on data from multiple sources (WHO 2021, LKCR 2022, NIL 2021)

Distribution by indications has been estimated based on a multinational LNG-IUS patient survey, which showed that 55% of removals were in patients where IUS was prescribed for heavy menstrual bleeding and the remaining 45% for contraception (Römer et al., 2009).

A summary of Levosert sales and removals from product launch until 2020 in the four study countries, the geographical distribution of OB-GYNs, the expected achievable sample of OB-

-

¹ Based on epidemiological survey of 23,885 LNG-IUS users (Backman et al., 2001).

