# of total patients / month	

- **Q2.** Approximately, how many of your patients are **currently using** one of the following types of contraception by indication?
 - ✓ Oral/pill
 - ✓ Intrauterine device (IUD)
 - ✓ Intrauterine system (IUS)
 - ✓ Hormonal ring
 - ✓ Implant
 - ✓ Injection

	Contraception only	Heavy menstrual bleeding (with and without intended contraception)
# of patients currently using any of the above treatment types	#	#

Q3. Considering **all your patients by indication,** approximately what percentage are currently using the different types of contraception listed below?

	Contraception only	Heavy menstrual bleeding (with and without intended contraception)
Oral/pill	%	%
Intrauterine device (IUD)	%	%
Intrauterine system (IUS)	%	%
Hormonal ring	%	%
Implant	%	%
Injection	%	%
Total	100%	100%

Q4. Considering all your patients currently using intrauterine systems (IUSs) by indication, approximately what percentage are using Levosert (levonorgestrel)?

	Contraception only	Heavy menstrual bleeding (with and without intended contraception)
Proportion of patients currently using IUSs who receive Levosert	%	%

Q5. Considering **all** your patients ever having used and/or currently using **Levosert (levonorgestrel)**, what is the age distribution at the time of prescription, by indication?

	Contraception only	Heavy menstrual bleeding (with and without intended contraception)
16-24 years of age	%	%
25-34 years of age	%	%
35-44 years of age	%	%
45-54 years of age	%	%
55+ years of age	%	%
Total	100%	100%

Q6. When using **Levosert (levonorgestrel)** for **heavy menstrual bleeding (with and without intended contraception)**, what is the average time from insertion to achieving treatment effectiveness (defined as significant reduction in menstrual blood loss)?

1	Less than one month	
2	One to less than two months	
3	Two to less than three months	
4	Three to less than four months	
5	Four months or more	

Q7. In your experience, approximately what percentage of patients using **Levosert (levonorgestrel)** for the following indications need to get it **removed (with or without replacement)** by the end of each year (cumulatively since insertion)?

Please note your responses must be cumulative over time (since insertion).

	Contraception only	Heavy menstrual bleeding (with and without intended contraception)
By the end of Year 1	%	%
By the end of Year 2	%	%
By the end of Year 3	%	%
By the end of Year 4	%	%
By the end of Year 5	%	%

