By the end of Year 6	%	%

VALIDATION MESSAGE REQUIRING TRANSLATION:

ERROR: Please note your responses for each column must be cumulative. For example, your response for the end of year 2 must be equal to or greater than your response for the end of year 1, etc.

Q8. For patients who use **Levosert (levonorgestrel)** for **contraception only** for more than six years, for approximately how many years in total do these patients typically use **Levosert (levonorgestrel)**?

Please feel free to provide a fractional number of years.

	# of years	RANGE 7-10
--	------------	------------

Q9. For patients who use **Levosert** (**levonorgestrel**) for **heavy menstrual bleeding** (with and without **intended contraception**) for more than six years, for approximately how many years in total do these patients typically use **Levosert** (**levonorgestrel**)?

Please feel free to provide a fractional number of years.

	# of years	RANGE 7-10
--	------------	------------

13-02-2023

Q10. Among your patients using Levosert (levonorgestrel) for heavy menstrual bleeding (with and without intended contraception), what percentage would continue to show treatment effectiveness by the end of each year (cumulatively since insertion), while continuing to use the same Levosert (levonorgestrel) device.

Please note your responses must be cumulative over time since insertion.

Treatment effectiveness is defined as significant reduction in menstrual blood loss.

		Heavy menstrual bleeding (with and without intended contraception)
1	By the end of Year 1	%
2	By the end of Year 2	%
3	By the end of Year 3	%
4	By the end of Year 4	%
5	By the end of Year 5	%
6	By the end of Year 6	%
7	Beyond 6 years	%

VALIDATION MESSAGE REQUIRING TRANSLATION:

ERROR: Please note your responses for each column must be cumulative. For example, your response for the end of year 2 must be equal to or less than your response for the end of year 1, etc.

Q11. Considering **all** your patients ever having used and/or currently using **Levosert (levonorgestrel)** for the following indications and who had it removed (with or without replacement), approximately what percentage of these patients had **Levosert (levonorgestrel)** removed for each of the following reasons?

	Contraception only	Heavy menstrual bleeding (with and without intended contraception)
Removed per Schedule (IUS Expiry)	%	%
Planning for family	%	%
Side effects	%	%
Lack of effectiveness	%	%
Menopausal	%	%
Other (specify)	%	%
Total	100%	100%

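### The primary endpoint formula in section 10.1 credits each removal in Year i with i full years, so its Years 1-6 part is an upper bound, not an expected value

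*Protocol*

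**What the plan says.** Protocol section 10.1 first defines the quantity of interest: "Duration of Levosert usage is defined as the difference in time between removal (with or without replacement) and insertion of the device". That is elapsed time. Because no patient-level data are collected, the section then fixes an aggregate calculation: "expected duration of Levosert usage for each indication will be calculated as follows". The likelihood of removal in Year i is weighted by i and summed over Years 1 to 6. To this is added "likelihood of Levosert removal beyond Year 6 x total expected usage duration in those patients".

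The protocol does not name the survey item that supplies the yearly likelihoods, but only one can. Q7 in Appendix 3 asks for the percentage of patients whose device is removed "by the end of each year (cumulatively since insertion", for Years 1 to 6. Its validation message requires that "your response for the end of year 2 must be equal to or greater than your response for the end of year 1". The likelihood for Year i is thus the difference between two successive cumulative percentages. When in the year removals occur is not asked.

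The last term comes from Q8 and Q9, which ask for total years of use, allow fractions and accept 7 to 10.

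The protocol gives no within-year correction, no reason for weighting by i, and no alternative version of the calculation.

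**The concern.** A removal counted in Year i happened somewhere between i-1 and i years after insertion. The formula gives it the upper end of that interval: a device removed at month 2 counts as 1 year, and one removed at 2.1 years counts as 3. The final term, by contrast, uses reported elapsed years, so the formula adds a rounded-up year index to a real duration.

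The error for Years 1-6 has one direction only, towards longer use. Section 5 explains that the study was committed to a regulator because data on longer use in the bleeding indication are lacking, so this is the direction in which the primary result should be most carefully protected. A larger sample does not reduce the error, and the 95% confidence interval planned in section 10.3 does not reflect it.

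The subgroup comparisons in section 10.4 are also affected, because the error grows with F6. Under even spread, a group with F6 of 0.80 is inflated by 0.400 years and one with 0.45 by 0.225 years. A difference of 0.400 - 0.225 = 0.175 years would be lost from a comparison in which the first group has the shorter use.

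This is not a detail left to an analysis plan, since section 10.1 itself prescribes the formula.

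**Working it through.** **The plan's own figure.** The protocol states no numeric expected duration, so there is none to reproduce. Its only planning total, 821 removals in Table 3 of Appendix 1, adds up (227 + 429 + 69 + 96 = 821) but does not enter this point.

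**Inputs.**
- Appendix 1 gives "LNG-IUS user retention after 1 to 5 years of usage as reported by a post-marketing study: 0.94, 0.87, 0.82, 0.76, 0.65, respectively". Cumulative removal F(i) at Years 1 to 5 is therefore 0.06, 0.13, 0.18, 0.24, 0.35. These are planning figures, used here only to illustrate.
- Yearly likelihoods p(i) = F(i) - F(i-1): 0.06, 0.07, 0.05, 0.06, 0.11 for Years 1 to 5.
- F6 is not given. Cumulative removal cannot fall, so F6 is at least 0.35 on these figures. Values of 0.45, 0.60 and 0.80 are assumptions.
- Duration in users beyond Year 6 (T) is not given. T = 7, the lowest value Q8 and Q9 accept, is an assumption. It cancels from every difference below.

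**Formulas.**
- Protocol: D(i) = sum of i x p(i) + (1 - F6) x T
- Midpoint: D(mid) = sum of (i - 0.5) x p(i) + (1 - F6) x T
- Start of year: D(i-1) = sum of (i - 1) x p(i) + (1 - F6) x T
- Hence D(i) - D(mid) = 0.5 x F6 and D(i) - D(i-1) = F6.

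**Years 1-5 alone.** Sum of i x p(i) = 0.06 + 0.14 + 0.15 + 0.24 + 0.55 = 1.14. Overstatement under even spread = 0.5 x 0.35 = 0.175, or 0.18 years.

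**With Year 6 and the tail.** p(6) = F6 - 0.35.

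| F6 (assumed) | D(i) = 1.14 + 6 x p(6) + 7 x (1 - F6) | 0.5 x F6 | D(mid) | D(i-1) | Overstatement as % of D(mid) |
|---|---|---|---|---|---|
| 0.45 | 1.14 + 0.60 + 3.85 = 5.59 | 0.225 | 5.365 | 5.14 | 4.2 |
| 0.60 | 1.14 + 1.50 + 2.80 = 5.44 | 0.300 | 5.14 | 4.84 | 5.8 |
| 0.80 | 1.14 + 2.70 + 1.40 = 5.24 | 0.400 | 4.84 | 4.44 | 8.3 |

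**Without even spread.** If every removal falls exactly at a year end, the overstatement is 0. If every removal falls just after an anniversary, it approaches F6 x 1 year.

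**Late removals at year end.** If all Year 5-6 removals fall at year end and Years 1-4 are even, the overstatement is 0.5 x F(4) = 0.5 x 0.24 = 0.12 years, whatever F6 is. In that scenario the midpoint version understates by 0.5 x (F6 - 0.24) = 0.105, 0.18 or 0.28 years for F6 of 0.45, 0.60 or 0.80.

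**The case against.** The best defence is that the formula is an openly approximate summary in a descriptive study with no hypotheses and no decision threshold for duration. Items 14 and 15 in section 10.3 report the yearly removal percentages and the duration beyond six years, so a reader could approximately recompute the endpoint under another convention. This bears on severity and is accepted there. It does not repair the headline figure. The lack of patient-level data explains why an approximation is needed, not why the upper end of each interval was chosen.

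The second defence is stronger. Recommended durations are in whole years, and Q11 lists removal on schedule as a reason, so removals in late years may well cluster at year ends. The planning retention drops most in Year 5 (0.76 to 0.65). In the scenario worked above, the midpoint errs low by about as much as the protocol formula errs high at F6 of 0.45 (0.105 against 0.12 years), and by more at 0.60 and 0.80. The scheduled share is unknown, so this is a scenario only, but it stands as a reason not to report the midpoint alone. Q11 cannot settle it: it gives one overall share per indication, neither by year nor limited to the first six years.

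A reader might infer that half a year is the largest possible error. It is the ceiling only if removals are evenly spread within years and all devices are out by the end of Year 6. A reader might also infer that the i and i-1 versions bound the whole endpoint. They bound only its Years 1-6 part. The tail rests on Q8 and Q9, which cannot record total use between 6 and 7 years.

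**Conclusion.** The point holds. Section 10.1 defines duration as elapsed time and then computes, for Years 1-6, an upper bound labelled as an expected value. That defect and its direction follow from the formula and Q7 alone.

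The size depends on timing within the year, which the survey does not collect. Under even spread it is 0.5 x F6 years. The figure of at least 0.18 years also rests on the planning retention applying to these patients, and the larger figures on the assumed F6 values. The overall range is 0 to just under F6 x 1 year.

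A reader might infer that the correction would overturn a finding of use beyond three years. The documents do not support that: no threshold is set, and the illustrative midpoint estimates with a 7-year tail (4.84 to 5.365 years) remain well above three. Nor do they show that the midpoint is the true value; it is a more neutral convention with a stated assumption. For these reasons, and because the correction can be made at analysis, this is a should-fix point.

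**What to change.** In section 10.1:

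1. Replace i with the interval midpoint (i - 0.5) for removals in Years 1 to 6, and state the assumption that removals are spread evenly within years.
2. Report the i and i-1 versions beside it, labelled as upper and lower bounds for the Years 1-6 component only.
3. Add a sensitivity version that places late removals, for example those in Years 5 and 6, at year end. State that the choice of years is an assumption, since Q11 does not assign scheduled removals to years.

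Any analysis plan should carry the same text. The cost is a few lines of wording and two or three extra calculations from data already collected, with no change to the questionnaire. The downside for the sponsor is that the reported duration becomes slightly shorter.
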